**8.7. Pharmacokinetics**

Plasma samples will be used to evaluate the PK of JNJ-3989 (ie, JNJ-3976 and JNJ-3924), and, optionally, JNJ-6379, NA and/or PegIFN- $\alpha$ 2a, as applicable. Serum collected for PK may additionally be used to evaluate safety or efficacy aspects that address concerns arising during or after the study period. Genetic analyses will not be performed on these samples. Participant confidentiality will be maintained.

**8.7.1. Evaluations**

Venous blood samples will be collected for measurement of plasma concentrations of JNJ-3976, JNJ-3924, NA (ETV, TAF, or tenofovir) and PegIFN- $\alpha$ 2a, as applicable, at time points specified in the [Schedule of Activities](#). Bioanalysis of NA and PegIFN- $\alpha$ 2a is optional at the discretion of the sponsor. Bioanalysis of JNJ-6379 may also be done on samples collected from participants who received JNJ-6379 up to Protocol Amendment 4.

All participants will have sparse PK sampling on Day 1 and at Weeks 4, 12, and 24 (and at early withdrawal). All participants who consent to participate in the intensive PK substudy (optional)

will undergo intensive PK sampling at Week 4. If necessary (eg, for operational reasons), this visit may be scheduled at Week 8, 12, or 16.

### **8.7.2. Analytical Procedures**

#### **Pharmacokinetics**

Plasma samples will be analyzed to determine concentrations of JNJ-3976 and JNJ-3924 using a validated, specific, and sensitive liquid chromatography-fluorescence hybridization method under the supervision of the sponsor.

At the sponsor's discretion, plasma samples may be analyzed to determine concentrations of JNJ-6379 and/or NA and/or PegIFN- $\alpha$ 2a using a validated, specific, and sensitive liquid chromatography-mass spectrometry method under the supervision of the sponsor.

Plasma PK samples may be stored for future exploratory analysis of protein binding or the metabolite profile. Genetic analyses will not be performed on these plasma samples. Participant confidentiality will be maintained.

### **8.7.3. Pharmacokinetic Parameters and Evaluations**

#### **Parameters**

Plasma concentration-time data for JNJ-3989 (ie, JNJ-3976 and JNJ-3924) and, optionally, JNJ-6379, NA and/or PegIFN- $\alpha$ 2a will be analyzed via noncompartmental methods for all participants who underwent intensive PK sampling. The main PK parameter will be area under the plasma concentration-time curve over 24 hours (AUC24h), Cmax, tmax, plasma trough concentration (C0h), plasma concentration at the end of the dosing interval ( $\tau$ ) (C $\tau$ ), and minimum plasma concentration (Cmin). Additional exposure parameters may be calculated if applicable.

Data from this study may be combined with data from a selection of Phase 1 and 2 studies via population PK modelling. Individual estimates of PK parameters may be generated from the population PK analysis for potential use in exposure-response analysis.

## **8.8. Pharmacokinetics/Pharmacodynamics**

Relationships of individual PK parameters for JNJ-3976, JNJ-3924, and, optionally, JNJ-6379, NA and/or PegIFN- $\alpha$ 2a, with selected liver and blood biomarkers, and/or with selected safety endpoints may be evaluated.

## **8.9. Host Genetics**

A pharmacogenomic blood sample will be collected (preferably at baseline) to allow for the identification of genetic factors that may influence the efficacy, safety, or PK of the study intervention, to identify genetic factors associated with HBV infection, or to develop assays for the study intervention or HBV infection.

A blood sample will be taken for HLA typing as indicated in the [Schedule of Activities](#). In addition, host DNA blood samples to allow for epigenetic analyses will be collected.

## 8.10. Host Biomarkers

The study includes collection of blood samples for exploratory analysis of host blood biomarkers at the host RNA, protein, and cell level. Sampling will be performed in all participants at the time points indicated in the [Schedule of Activities](#).

Samples can only be used for research related to study intervention or HBV infection or may be used to develop tests/assays related to study intervention or HBV infection.

Blood samples will be taken at the time points indicated in the [Schedule of Activities](#) which can be used to explore immunogenicity of JNJ-3989. The emergence of antibodies to JNJ-3989 (antidrug antibodies) might be analyzed using assays such as an enzyme-linked immunosorbent assay.

## 8.11. Medical Encounters

Eventual medical encounters will be collected in the CRF by the investigator and study site personnel for all participants throughout the study.

# 9. STATISTICAL CONSIDERATIONS

Statistical analysis will be done by the sponsor or under the authority of the sponsor. A general description of the statistical methods to be used to analyze the efficacy and safety data is outlined below. Specific details will be provided in the Statistical Analysis Plan.

The primary analysis will be performed at the time when all participants have completed Week 48 or discontinued earlier. The final analysis will be performed when all participants have completed the last study visit (Follow-up Week 48) or discontinued earlier. For the IAs, please refer to Section [9.5](#).

### 9.1. Statistical Hypotheses

As this is an exploratory study, no hypothesis will be tested.

### 9.2. Sample Size Determination

This study aims to enroll 18 to 24 participants in total across Panels 1 and 2, ie, 8 to 12 participants per study panel.

Due to the exploratory nature of the study, the sample size was determined based on clinical and feasibility considerations related to the liver biopsy procedures performed multiple times during the study, rather than a formal statistical calculation. Nevertheless, a sample size of 8 to 12 participants each in Panel 1 and 2 is considered sufficient to provide adequate precision of the estimate of the primary endpoint (change from baseline to Week 40 in the proportion of HBsAg-positive hepatocytes) as estimated by the 80% confidence interval (CI).

For the estimation of the absolute change in the proportion of HBsAg-positive hepatocytes from baseline to Week 40 for the overall study population (Panels 1 and 2 combined), the following assumptions were made. Assuming an absolute reduction of 70% in Panel 1 (75% at baseline

versus 5% at Week 40) and 29% in Panel 2 (30% at baseline versus to 1% at Week 40), and assuming an inter-subject variability of the change equal to 0.5 on the logit scale in both panels, a binomial model including visit as covariate with normal random effects provides an expected width of the 80% CI of 16.7% for N 24, a width of 17.9% for N 20, and a width of 20.3% for N 16. The point estimates (two-sided 80% CI) are 50.8% (42.5%; 59.1%) with N 24, 50.7% (41.8%; 59.7%) with N 20, and 50.6% (40.5%; 60.8%) with N 16.

For the between-panel difference in the absolute reduction in the proportion of HBsAg-positive hepatocytes from baseline to Week 40 using the binomial model described above augmented with panel as an additional covariate and the same inter-subject variability, the estimated width of the two-sided 80% CI around the difference (Panel 1 – Panel 2) is 17.6% for N 24 (12 per panel), 19.3% for N 20 (10 per panel), and 21.2% for N 16 (8 per panel). The point estimates (80% CI) are 40.4% (31.5%; 49.2%) for N 24, 39.2% (29.6%; 48.9%) for N 20, and 39.4% (28.8%; 50.0%) for N 16.

In addition, N 20 would also be sufficient to provide adequate precision for a between-panel difference in the relative change from baseline of at least 26% in case of large inter-subject variability.

Assuming a drop rate of 20%, the sample size will be therefore set to 12 participants per panel for Panels 1 and 2.

### **9.3. Populations for Analyses**

For purposes of analysis, the following populations are defined:

Population	Description
Randomized	All participants who were randomized in the study
Enrolled	All participants who were enrolled in the study
Intent-to-treat (ITT)	All participants who were either randomly assigned or enrolled to an intervention arm and received at least 1 dose of study intervention. Participants will be analyzed according to the study intervention they were randomly assigned or enrolled to.
Safety	All participants who received at least 1 dose of study intervention. Participants will be analyzed according to the study intervention they actually received.

### **9.4. Statistical Analyses**

The Statistical Analysis Plan will include a more technical and detailed description of the statistical analyses described in this section. This section is a summary of the planned statistical analyses of the most important endpoints including primary and key secondary endpoints.

Given the exploratory nature of the study and the limited sample size per panel, no statistical testing will be performed. All data will be summarized descriptively including 80% confidence intervals as appropriate.

#### **9.4.1. Analysis of Efficacy and Antiviral Activity**

To evaluate the efficacy and antiviral activity in blood and liver, the primary analysis set will be the ITT population. Efficacy and antiviral activity will be assessed for participants in Panels 1

and 2. For all efficacy and antiviral activity endpoints, unless specified otherwise, the following comparisons will be addressed:

1. Overall population, pooling all participants regardless of panels.

Between Panels 1 and 2: HBeAg-positive patients who are not currently being treated versus HBeAg-negative patients being virologically suppressed by NA treatment.

All efficacy summaries will be presented with descriptive statistics, overall and by study panel.

If the endpoint is continuous, the descriptive statistics will include the number of participants, mean, standard deviation (SD), median, range, and interquartile range. If the endpoint is binary or categorical, the frequency distribution with the number and percentage of participants in each category will be calculated.

Graphic displays will also be used to summarize the data and to visualize trends by study panel.

Where applicable, additional specifics for analyses of primary, secondary, and exploratory endpoints are detailed below.

#### **9.4.1.1. Analysis of the Primary Endpoint**

The primary endpoint is the change between baseline and on-treatment liver biopsy (Week 40) in terms of the proportion of HBsAg positive hepatocytes. The primary endpoint will be summarized descriptively and modelled with an appropriate statistical model accounting for the number of hepatocytes sampled in each liver biopsy. The change from baseline will be summarized for the overall study population and within each panel, together with the between-panel difference in the change..

No imputation rule will be applied for the analysis on the ITT population since only complete cases will be considered. In addition, the treatment policy strategy will be followed to account for the occurrence of intercurrent events, such as treatment discontinuation prior to Week 40, ie, all biopsies collected at Week 40 will be used, regardless of occurrence of treatment discontinuation prior to Week 40. This strategy is supported by the small sample size, the exploratory nature of the study and ethical considerations.

In addition, a sensitivity analysis on the ITT population will be combining a treatment policy strategy with the Baseline Observation Carried Forward (BOCF) approach.

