- a. All study visits are to be scheduled relative to the baseline (Day 1) visit date.
- b. If necessary (eg, for operational reasons), the screening phase may be extended up to a maximum of 6 weeks in agreement with the sponsor.
- c. Day 1 samples are to be collected before the first dose of study intervention.
- d. End of study intervention. If NA treatment completion criteria are not met at Week 48 (see Section 6.6.1), participants will continue NA treatment during the follow-up phase. Participants who discontinue study intervention early will have an early WD visit and will enter follow-up (see the [Schedule of Activities - Follow-up Phase](#)) unless they withdraw consent. Participants who withdraw consent will be offered an optional safety follow-up visit to occur on the day of consent withdrawal. For the optional safety follow-up visit, assessments are at the investigator's discretion and could be similar to the early WD visit.
- e. The ICF must be signed before the first study-related activity.
- f. If participants agree to undergo an optional liver biopsy, they must sign a separate ICF at screening or at any time prior to the optional liver biopsy (which may take place at Follow-up Week 24, or at any time during the study when clinically indicated). Refusal to give consent for these optional liver biopsy samples does not exclude a participant from participation in the study.
- g. Minimum criteria for the availability of documentation supporting the eligibility criteria will be described in Section 10.3, Appendix 3, Regulatory, Ethical and Study Oversight Considerations. Clinical status will be checked at screening and again before the first liver biopsies at Week -1 and before the first dose of study intervention. If a participant's clinical status changes (including any available laboratory results or receipt of additional medical records) after the start of screening but before the first liver biopsies at Week -1 or before the first dose of study intervention is given such that he or she no longer meets all eligibility criteria, then the participant should be excluded from participation in the study. Retesting to assess eligibility will be allowed once, using an unscheduled visit during the screening period.

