- An optional liver biopsy (core liver biopsy and/or FNAB) may be performed at Follow-up Week 24 or at any time during the study if the participant provided consent.
- No JNJ-3989 will be administered or dispensed during follow-up. Administration/Dispensation of NA is only applicable for participants who could not stop NA treatment at Week 48 (Section 6.6.1), or for those who met the NA re-treatment criteria (Section 6.6.2). In between study visits, participants will take NA treatment at home. Participants will be requested to bring their NA treatment with them to each study visit. At study visits, the NA treatment should be taken on site.
- Vital signs include supine SBP, DBP, pulse rate, and body temperature.
- All ECGs will be read centrally; ECGs should be completed before any tests, procedures or other consultation for that visit.
- A liver ultrasound is recommended approximately every 24 weeks for HCC screening.
- Following local standard practice the biopsy location will be identified with ultrasound (which will also be used to rule out contraindicating conditions for a biopsy) and after application of local anesthesia the FNAB samples and core liver biopsy samples will be collected. Prior to the biopsy, blood coagulation and platelets will be assessed at a local laboratory according to local practice. The (post)biopsy visit can either occur during a regularly scheduled visit or an unscheduled visit.

- j. Biochemistry samples must be taken after fasting for at least 10 hours for measurement of phosphate, calcium, creatinine, and lipids.
- k. Creatinine clearance (eGFR calculated by the CKD-EPI formula) will be assessed.
- l. ALT/AST elevations (ie, ALT and/or AST  $\geq 3$ x ULN and  $\geq 3$ x nadir [ie, lowest value during study participation]), should trigger an assessment of confounding factors (alcohol intake, change in concomitant medication, and comorbidities) and a confirmatory visit, to be scheduled preferably within 7 days of the receipt of the initial ALT/AST results, to repeat laboratory testing of AFP, ALT, AST, ALP, bilirubin (total and direct), INR, albumin, and HBV DNA until ALT and AST levels have returned to  $<5$ x ULN and HBV DNA is  $<20,000$  IU/mL. Additional tests should be considered based on clinical judgement. For more details and further management guidance refer to Section 8.5.6.2 and Section 10.6.
- m. Liver function tests only.

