**Note:** Participants who develop a neuropsychiatric AE during optional PegIFN- $\alpha$ 2a treatment, will be monitored closely until the neuropsychiatric AE resolves, with frequent (at least weekly) follow-up phone calls.

- Participant develops colitis symptoms (such as but not limited to abdominal pain, bloody diarrhea, and fever)
- Participant develops symptoms or signs suggestive of pancreatitis

If a participant discontinues investigational intervention for any reason before Week 48, then the early withdrawal assessments should be obtained. The participant will enter the follow-up phase and complete the follow-up schedule unless the participant withdraws consent. Participants who withdraw consent will be offered an optional safety follow-up visit to occur on the day of consent withdrawal. Study intervention assigned to the participant who discontinued study intervention may not be assigned to another participant.

In case a participant withdraws consent for the second biopsy, the study participant may continue the study intervention and visit schedule as outlined in the [Schedule of Activities](#).

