5. STATISTICAL ANALYSES

5.1. General Considerations

5.1.1. Analysis Phase

The analysis phases are defined in [Table 1](#) below. Note that the screening, open-label, and follow-up phases are non-overlapping and cover the entire study period. The optional PegIFN- α 2a treatment phase, in contrast, may overlap with both the open-label and follow-up phases.

Table 1: Analysis Phases Start and End Dates

Analysis phase	Start date	End date
Screening	The date of signing the informed consent	1 day before the first study agent intake (JNJ-3989 or JNJ-6379)
Open-label study intervention	Date of first study agent intake (JNJ-3989 or JNJ-6379)	Earliest of the following dates: 
 • Early discontinuation date for JNJ-3989 + 5 days^a • Study termination date • Max{ 
 • Date of last JNJ-3989 intake, • Date of Week 48 visit • } + 5 days^a • Cut-off date^b
Follow-up	End date of open-label phase + 1 day	Min (study termination date, study completion date, cut-off date ^b)
Optional PegIFN- α 2a treatment	Date of first PegIFN- α 2a intake	Min (Date of last PegIFN- α 2a intake + 5 days ^a , cut-off date ^b)

a : Addition of 5 days is only applicable for Adverse Events and Concomitant Medications.

b : Cut-off dates will be defined to match the prespecified timepoints for interim analyses, the primary analysis and the final analysis, respectively.

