5.1.2. Visit Windows

As participants do not always adhere to the protocol visit schedule, visits will be allocated within each phase to an analysis time point based on the time intervals in [Table 2](#).

If a participant has two or more actual visits in a visit window (“time interval” in [Table 2](#)), only one will be selected as the protocol visit according to the following rules:

1. The measurement closest to the target day will be used.
2. If the measurements fall equidistant from the target day, the last measurement in chronological order will be used.
3. If there are two or more measurements on the same day, then the last measurement in chronological order will be used. If the time of the assessment is not available, the highest record/sequence number will be selected.

Only the protocol visits will be included for calculating summary statistics across participants within a time point or for statistical models using longitudinal data. However, listings or figures

of individual participant-level data (including spaghetti plots), or analyses that identify a maximum or minimum value across time points (e.g., maximum ALT value), may include all measurements.

End of treatment (i.e., EOT) and end of study (i.e., EOS) time points will be included in all analysis over time unless stated otherwise.

Special rule for Follow-up Week 48 (FU W48): Note that the time interval for FU W48 is open on the right, $[324, +\infty)$, while the next time interval is $[352, 379]$. Any visit in follow-up days $[324, 351]$ will be assigned to FU W48. If a patient does not have a visit date in that interval but does have visits on or after follow-up day 352, then the earliest such visit will be assigned to FU W48. Any additional visits on or after follow-up day 352 will be assigned to an “Ext” follow-up visit according to [Table 2](#).

Table 2: Visit Windows

a) Screening and Open-Label Phases

Analysis phase	Target day	Analysis time point (Week)	Analysis time point (Label)	Open-label time interval (Days)
Screening	$-\infty$	-1	Screening	<0
Open-Label	1	0	Baseline	Pre-dose: 1
	15	2	Week 2	$[2, 22]$
	29	4	Week 4	$[23, 43]$
	57	8	Week 8	$[44, 71]$
	85	12	Week 12	$[72, 99]$
	113	16	Week 16	$[100, 127]$
	141	20	Week 20	$[128, 155]$
	169	24	Week 24	$[156, 183]$
	197	28	Week 28	$[184, 211]$
	225	32	Week 32	$[212, 239]$
	253	36	Week 36	$[240, 267]$
	281	40	Week 40	$[268, 295]$
	309	44	Week 44	$[296, 323]$
	337	48	Week 48	$[324, 351]$

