Estimates of the absolute and relative changes from baseline in the proportion of HBsAg+ hepatocytes at Week 40 and associated 80% CIs will be obtained from the model as follows. Let p_0 and p_1 be the proportion of infected hepatocytes at times 0 (baseline) and 1 (Week 40) for a “typical” subject. Based on the binomial model, $p_0 = \text{expit}(\alpha)$ and $p_1 = \text{expit}(\alpha + \beta)$, where $\text{expit}(x) = \exp(x)/[1 + \exp(x)]$ is the inverse of the logit function. The absolute and relative changes from baseline are therefore

- Absolute change: $p_1 - p_0 = \text{expit}(\alpha + \beta) - \text{expit}(\alpha)$
- Relative change: $\frac{p_1 - p_0}{p_0} = \frac{p_1}{p_0} - 1 = \frac{\text{expit}(\alpha + \beta)}{\text{expit}(\alpha)} - 1$

SAS code to fit the binomial mixed model and estimate the quantities of interest is provided in [Attachment 3](#). We may also report estimates and CIs for p_0 and p_1 .

Additional models may be evaluated depending on the distribution of data (such as Poisson, Negative-Binomial or Zero-Inflated regression models) and comparison of fit statistics would be performed to select the most adequate model. Additional covariates may be added to the model based on clinical considerations.

All biopsy data will be used for this analysis, including data collected after treatment discontinuation or occurrence of major protocol deviations ([Appendix 4](#)) potentially affecting the primary endpoint (see [Attachment 2](#)).

5.3.1.2.2.2. Comparison Between Panels 1 and 2

Study panel will be included as an additional covariate in the model described in Section [5.3.1.2.2.1](#). That is, the model for $\text{logit}(p_{ij})$ will become

$$\text{logit}(p_{ij}) = \underbrace{[\alpha + \delta_\alpha I(\text{panel}_i = 1) + \xi_i]}_{\text{intercept}} + \underbrace{[\beta + \delta_\beta I(\text{panel}_i = 1) + \gamma_i] j}_{\text{slope}}$$

with:

- α : Fixed intercept for a “typical” Panel 2 subject
- δ_α : Fixed difference in intercepts (Panel 1 minus Panel 2) for “typical” subjects
- β : Fixed slope for a “typical” Panel 2 subject
- δ_β : Fixed difference in slopes (Panel 1 minus Panel 2) for “typical” subjects
- panel_i : Panel number (1 or 2) for subject i

All other aspects of the model are unchanged from the specification in Section [5.3.1.2.2.1](#).

The input data for this model are Y_{ij} , N_{ij} , panel_{*i*}, and *n*. There are six parameters to estimate: α , δ_α , β , δ_β , SD_{intercept}, and SD_{slope}.

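### For participants who stop JNJ-3989 before the Week 40 biopsy, the stated treatment-policy strategy has no scheduled biopsy and no usable SAP time-point label behind it

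*Protocol*

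**What the plan says.** **The strategy.** Protocol section 9.4.1.1 combines complete cases with treatment policy: "all biopsies collected at Week 40 will be used, regardless of occurrence of treatment discontinuation prior to Week 40". SAP section 5.3.1.2.2.1 agrees: "All biopsy data will be used for this analysis, including data collected after treatment discontinuation or occurrence of major protocol deviations". SAP section 5.3.1.2.1 requires evaluable hepatocyte counts at both baseline and Week 40.

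**What happens to discontinuers.** Footnote d of the Schedule of Activities (protocol 1.3.1) states: "Participants who discontinue study intervention early will have an early WD visit and will enter follow-up". Section 7.1 says of those who stop before Week 48: "The participant will enter the follow-up phase and complete the follow-up schedule unless the participant withdraws consent". The W48/WD column has no biopsy. In the follow-up table (1.3.2) the only biopsy is optional: "An optional liver biopsy (core liver biopsy and/or FNAB) may be performed at Follow-up Week 24". That footnote goes on to allow one at any other time in the study, given consent.

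**How the SAP labels visits.** Table 1 (section 5.1.1) ends the open-label phase at the earliest of several dates, one of which is the "Early discontinuation date for JNJ-3989". The five-day extension there covers only adverse events and concomitant medications. Follow-up starts the next day. Section 5.1.2 then says "visits will be allocated within each phase to an analysis time point based on the time intervals in" Table 2, where Week 40 exists only in the open-label part.

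**Sensitivity analyses.** SAP section 5.3.1.2.4.1 replaces a missing Week 40 count by the baseline count and names premature treatment discontinuation as one cause of missingness. Multiple imputation (5.3.1.2.4.2) is applied only to the descriptive secondary analysis.

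**The concern.** A treatment-policy estimate needs outcomes observed after discontinuation. For people who stop JNJ-3989 before the biopsy, the schedule does not call for that observation, and the labelling rules would set it aside if it were made. SAP Appendix 2 reports no change from the protocol-planned analyses, so a reader would take the treatment-policy description at face value.

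Two things are at stake. The first is what the estimate describes. Section 7.1 lists virologic breakthrough and ALT/AST elevations among the stopping triggers, so discontinuers may differ virologically. If they keep more HBsAg-positive hepatocytes, an analysis without them overstates the reduction relative to treatment policy. The second is reproducibility. One programmer following section 5.3.1.2.2.1 and another following Tables 1 and 2 could build different primary datasets, and under the second reading an observed biopsy would be overwritten by the baseline value in the sensitivity analysis.

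**Working it through.** **1. The plan's own figures.** With 20% loss, 12 × 0.8 = 9.6 per panel, matching the SAP's 9-10 usable. A logit-normal approximation to the SAP model (Scenario A, slope SD 0.5, intercept SD 1.0, 10,000 simulations) gives 80% CI widths for the overall absolute reduction of 16.5, 18.1 and 20.3 points at N = 24, 20 and 16. The stated widths are 16.7, 17.9 and 20.3. The figures reproduce, and nothing below changes them.

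**2. Can a biopsy after JNJ-3989 discontinuation be labelled Week 40?** The schedule places the biopsy at Day 281 ± 4 weeks, i.e. Days 253 to 309. Let D be the day JNJ-3989 stops and B the biopsy day, with B > D.

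- Table 1: open-label ends on day D, with no extension for biopsies, so B lies in follow-up, on follow-up day B − D.
- Example: D = 141 and B = 281 give follow-up day 140, which Table 2 labels Follow-up Week 20 (days 128-155).
- All pairs: D = 1 to 252 gives 252 × 57 = 14,364; D = 253 to 308 gives 56 + 55 + … + 1 = 1,596; total 15,960. The number labelled Week 40 is 0.

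**3. Can the optional biopsy fall at the right calendar time?** Yes. It is scheduled at follow-up day 169 ± 4 weeks, relative to the last JNJ-3989 dose. A last dose on study day L puts it on days L + 168 − 28 to L + 168 + 28. This overlaps Days 253-309 when L is between 253 − 196 = 57 and 309 − 140 = 169. It would still carry a Follow-up label.

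**4. Who is analysed under the literal reading?**

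| Participant | Phase at biopsy | In the primary analysis? |
|---|---|---|
| Stopped only JNJ-6379 (Amendment 5) | Open-label | Yes |
| Stops JNJ-3989 after the biopsy, before Week 48 | Open-label | Yes |
| Stops JNJ-3989 before the biopsy, no biopsy taken | – | No |
| Stops JNJ-3989 before the biopsy, biopsy taken | Follow-up | No by Tables 1-2; yes by section 5.3.1.2.2.1 |

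**5. Illustrative size.** The documents give no JNJ-3989 discontinuation rate, so 5%, 10% and 20% are assumptions. The 20% case is an upper one because the plan's drop rate covers all losses. Scenario A's overall reduction is (70 + 29) / 2 = 49.5 points. If a fraction d discontinues and their change lies anywhere between none and full, the treatment-policy mean lies between 49.5 × (1 − d) and 49.5.

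| d | Lowest treatment-policy mean | Largest gap | Chance of at least one among 24, 1 − (1 − d)^24 |
|---|---|---|---|
| 5% | 47.0 | 2.5 | 0.708 |
| 10% | 44.6 | 5.0 | 0.920 |
| 20% | 39.6 | 9.9 | 0.995 |

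For scale, the planned 80% CI half-width at N = 20 is 17.9 / 2 ≈ 9 points.

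**The case against.** The strongest reply is that the protocol promises to use Week 40 biopsies if they are collected; it does not promise to collect them. Treatment policy can coexist with missing data, and section 9.4.1.1 itself plans a sensitivity analysis pairing the two. This stands as far as collection goes. It does not answer the labelling conflict, which affects biopsies that were collected.

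A reader might infer that a biopsy after JNJ-3989 discontinuation is definitively excluded. The documents do not support that. Section 5.3.1.2.2.1 expressly includes such data, so the SAP contradicts itself. Table 2 applied literally would also label the Week -1 baseline biopsy Screening, which shows that the SAP has no biopsy-specific labelling rule. The follow-up footnote also permits a consented biopsy at any time, so collection is possible.

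The worst case is already visible: carrying baseline forward is exactly the assumption that discontinuers with a baseline biopsy show no change. Multiple imputation also restores them, though only descriptively. Neither uses a discontinuer's observed value.

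The size may well be small. The SAP's version history says the number of imputations was cut because missing data were limited. The model estimates a typical subject on the logit scale, so an average of percentage points only approximates any shift in the reported estimate. The study is exploratory, tests no hypothesis, and names the endpoint on-treatment Week 40.

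**Conclusion.** The documents state a treatment-policy strategy that, for pre-biopsy JNJ-3989 discontinuers, the schedule does not supply with data and the phase-based labels do not admit. As written, the primary analysis in effect describes participants still on JNJ-3989 at the Week 40 biopsy. This rests on applying Tables 1 and 2 to biopsies as they stand.

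A reader might go further and call the analysis completers-only. That is too broad: it includes those who stopped only JNJ-6379 and those who stop JNJ-3989 between the biopsy and Week 48.

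A reader might also scale the effect to Panel 1, getting 20% × 70 = 14 points, and set it against the 16.7-point CI width. That treats every loss as a JNJ-3989 discontinuer and uses the width of the overall estimate, not Panel 1's. The supportable statement is the overall range in the working: 0 to 2.5, 5.0 or 9.9 points, under assumed discontinuation rates. The point is worth correcting because a stated property of the primary analysis is not delivered, not because a bias has been shown.

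**What to change.** 1. **SAP 5.1.1 and 5.1.2.** Exempt liver biopsies from the phase split and assign the Week 40 biopsy by days since Day 1, whatever the JNJ-3989 status. Section 5.3.1.2.2.1 can then be carried out, and the baseline-carried-forward analysis never overwrites an observed biopsy. The day interval should be the schedule's own (Days 253-309, 57 days). Table 2's Week 40 window (Days 268-295, 28 days) would leave out 29 permitted days even for participants on treatment.
2. **Reporting.** Give, per panel, the number of participants who stopped JNJ-3989 before the Week 40 biopsy, with and without a biopsy. If none has one, describe the primary estimate as applying to participants on JNJ-3989 at the Week 40 biopsy rather than as treatment policy.
3. **Reconcile the protocol.** Footnote d, section 7.1 and section 9.4.1.1 need to agree. Whether discontinuers keep the biopsy visit is for the sponsor to decide: for them it would be an invasive research procedure not currently scheduled, and adding it would need a protocol amendment.

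Items 1 and 2 cost a short SAP rule and a count table. They require no new biopsies and can be done after biopsy collection has ended. If the estimate is restated, the cost is a narrower claim.
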